Sample size and power considerations

The sample size calculation applies jointly to both primary efficacy objectives. A power analysis for comparing two proportions using Pearson’s chi-square test indicated that, with a 1:15 allocation ratio between groups, a total sample size of 992 would provide 92% power to detect a 20 percentage point absolute difference (0.80 vs. 0.60) at a two-sided significance level of 5% ($\alpha = 0.05$). The calculation employed a normal approximation to the binomial distribution under the null hypothesis of no difference in proportions. For practical and operational considerations, the sample size was rounded up to 1000 participants to ensure sufficient power and account for potential deviations.

Framework

Both primary and secondary outcomes are analysed within a superiority framework; surgical interventions are favourable compared to non-surgical interventions.

Statistical interim analysis and stopping guidance

No statistical interim analysis is planned on the primary endpoint.

Timing of final analysis

Data extraction and analysis for the between-group comparison (Surgical vs. Non-Surgical) for the primary endpoint (1 year follow-up) is planned to be performed after making this SAP public available. The main publication of the trial will be prepared when these data have been received and cleaned (anticipated by September 2025).

Timing of outcome assessments

The overview of trial procedures and time-point of each outcome assessment is presented in the **Illustration 2** “Timeline for recruitment and follow-up” and **Box 1** “Outcomes and Covariates – Timepoint of assessment”. The Treatment allocation date (Surgical or Non-surgical) is used to calculate 3 months, 6 months and 1 year follow-up time points.

[figure not shown]

Illustration 2: Timeline for recruitment and follow-up. -t₂: 2-4 days prior to medical examination; -t₁=Day of medical examination; t₀=Allocation; t₁= 3 months; t₂= 6 months; t₃= 1 year.

STATISTICAL PRINCIPLES

Confidence intervals and p-values

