All statistical tests and 95% confidence intervals (95%CIs) will be two-sided and *p-value* < 0.05 will be considered statistically significant for the primary and co-primary endpoint. Groups will be considered comparable if the two-sided 95% confidence interval for the odds ratio comparing Shoulder Surgery with Nonoperative Treatment, for both the primary and co-primary endpoint, lies entirely within the range of 0.80 to 1.25.²⁷ In the secondary outcomes Quick-DASH and VAS, a 95% confidence interval excluding a difference greater than 10 Quick-DASH points or 10 points on VAS between the two groups will be interpreted as indicating absence of a minimal clinically important difference (i.e. possible equivalence).

To address multiplicity, a gatekeeping procedure will be applied to both the primary objectives and the key secondary objectives to determine which will be used in the interpretation of the study results. While all outcomes will be analysed and presented, only those passing the gatekeeping procedure will be considered for inferential conclusions. The gatekeeping procedure follows a hierarchical approach in the prioritised order listed below. Statistical testing will proceed sequentially until an analysis fails to show a statistically significant difference (*p* < 0.05), or until all analyses have been completed.

If a test does not meet the specified statistical significance threshold, no further claims will be made for subsequent outcomes in the hierarchy:

- 1) PASS
- 2) Quick-DASH MIC
- 3) GPE
- 4) Quick-DASH

- 5) Maximum Pain
- 6) Pain in activity
- 7) Pain at rest
- 8) Shoulder related sleep disturbance

Adherence and protocol deviations

Adherence to the surgical intervention is assessed by the percentage of patients being referred to surgery at the initial clinical evaluation, and the actual number of these patients having a record of the surgery was performed in the REDCap database, including date and type of surgery performed: adherence% = (Number of patients with a surgical record in REDCap database/ number of patients referred for surgery at first medical examination) x 100.

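### The 92% power applied jointly to both primary objectives is the power of one test; under the fixed testing sequence the power to claim Quick-DASH MIC, and so both objectives, is about 85–89%

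*SAP*

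**What the plan says.** The section Sample size and power considerations opens with: "The sample size calculation applies jointly to both primary efficacy objectives". It then describes one calculation, for a single chi-square comparison: "with a 1:15 allocation ratio between groups, a total sample size of 992 would provide 92% power". The planning values are 0.80 against 0.60, tested two-sided at 5%. On the variance it says: "The calculation employed a normal approximation to the binomial distribution under the null hypothesis of no difference in proportions". The total is rounded up to 1000. The section gives no separate rates for the second endpoint, no correlation between the endpoints and no probability of succeeding on both.

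The section Confidence intervals and p-values sets the decision rule. PASS is first in the hierarchy and Quick-DASH MIC second, each tested at p < 0.05. The consequence of a failed step is explicit: "If a test does not meet the specified statistical significance threshold, no further claims will be made for subsequent outcomes in the hierarchy".

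**The concern.** The two sections do not fit together for the second primary objective. The calculation concerns one comparison of two proportions, yet it is said to serve both objectives jointly. Under the hierarchy, Quick-DASH MIC can never support a claim by itself: PASS must be significant too. The power to claim Quick-DASH MIC is therefore the probability that both tests are significant, which is also the power to establish both objectives. It is smaller than the power of either test unless the two test statistics are perfectly correlated.

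What is at stake is how the design is described. A reader who takes 92% as the chance of establishing both objectives, when both true effects are as planned, would put the chance of falling short at 8%. Under the SAP's own planning values it is larger. The gap matters most when Quick-DASH MIC is nominally significant but cannot be claimed because PASS failed; the printed power makes no allowance for that outcome.

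**Working it through.** **Inputs from the SAP.** Total N = 992 at 1:15, so 62 surgical and 930 non-surgical patients; rates 0.80 and 0.60; two-sided α = 0.05; normal approximation with the null variance. The rounded total of 1000 gives 62.5 and 937.5. The hierarchy is PASS, then Quick-DASH MIC, each at 0.05.

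**Input not in the SAP.** The correlation ρ between the two test statistics. It is varied below.

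**Step 1: reproduce the printed figure.**

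- Pooled rate: (0.80 + 15 × 0.60)/16 = 0.6125.
- SE under the null: √[0.6125 × 0.3875 × (1/62 + 1/930)] = 0.0639.
- SE under the alternative: √[0.80 × 0.20/62 + 0.60 × 0.40/930] = 0.0533.
- Power: Φ[(0.20 − 1.96 × 0.0639)/0.0533] = Φ(1.40) = 0.9197.

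This is the SAP's 92%. Exact enumeration of the uncorrected chi-square test gives 0.917. At N = 1000 the formula gives 0.9219. The printed number is therefore right as the power of one test.

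**Step 2: power under the hierarchy.** PASS is tested first at the full 5%, so its power is the figure from step 1. For Quick-DASH MIC the claim requires both tests to be significant:

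P(both) = Φ₂(z, z; ρ), with z = Φ⁻¹(marginal power),

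where Φ₂ is the bivariate normal distribution function and both endpoints are given the SAP's rates. At ρ = 0 this is the square of the marginal power: 0.9197² = 0.846.

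| ρ | N = 992 | N = 1000 |
|---|---|---|
| 0 | 84.6% | 85.0% |
| 0.3 | 85.5% | 85.8% |
| 0.5 | 86.3% | 86.7% |
| 0.7 | 87.5% | 87.8% |
| 0.8 | 88.3% | 88.6% |
| 0.9 | 89.3% | 89.6% |
| 1 | 92.0% | 92.2% |

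The chance of not establishing both objectives at N = 992 is thus 100 − 84.6 = 15.4% at ρ = 0, 13.7% at ρ = 0.5 and 10.7% at ρ = 0.9, against 8.0% for a single test. Rounding up to 1000 adds about 0.3 to 0.4 points over ρ = 0 to 0.9 and does not close the gap.

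**Step 3: power for Quick-DASH MIC once PASS has succeeded.** Dividing P(both) by the marginal power at N = 992: 0.8459/0.9197 = 92.0% at ρ = 0, 0.8632/0.9197 = 93.9% at ρ = 0.5, and 0.8933/0.9197 = 97.1% at ρ = 0.9. The loss arises entirely from trials in which PASS fails and the second test is blocked.

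**The case against.** The best defence is about wording. The sentence says that the calculation, not the power, applies jointly, and the next sentence ties 92% to one comparison. A natural reading is that one calculation with common rates serves each binary endpoint. On that reading no printed number is wrong: 92% is the correct marginal power of each test. This stands, and it is why the point concerns what the figure is attached to and not an arithmetic mistake. It does not remove the point, because the written rule never lets Quick-DASH MIC be claimed on its own marginal test.

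Three stronger readings should be resisted.

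- **That the trial's success requires both endpoints.** The documents do not say so. The rule is a fixed sequence, and Trial design names PASS alone as the primary endpoint. PASS keeps its 92%.
- **That a result with PASS significant and Quick-DASH MIC not significant would be read against too high a power.** Step 3 shows the opposite: given success on PASS, the power for the second test is 92% or more for any non-negative correlation.
- **That the power for both is a fixed 85–87%.** That range corresponds to correlations from 0 to about 0.6. Both endpoints are patient reports on the same shoulder at one year, and the SAP gives no reason to stop at 0.6.

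It can also be said that the replacement figures do not describe the planned analysis exactly, since the SAP uses weighted logistic regression with stratification covariates and counts missing binary outcomes as non-response. That is true. The same limitation applies to the printed 92%, and the figures should be labelled accordingly. Finally, last follow-up was in January 2025, so the point cannot affect recruitment, and it changes no estimate or test.

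**Conclusion.** The concern holds in a limited form. The 92% is correct as the marginal power of a single chi-square test and, under the hierarchy, as the power for PASS. It is not the power to claim Quick-DASH MIC or to establish both primary objectives. That power is about 85–89% at N = 992 over correlations from 0 to 0.9, roughly 3 to 7 points lower (92.0 − 89.3 = 2.7; 92.0 − 84.6 = 7.4), and equals 92% only at correlation 1.

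The direction is certain for any correlation below 1; the size is not. It rests on an assumed correlation, on 0.80 against 0.60 for both endpoints, and on no loss from weighting, missing data or crossover.

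A reader might infer that the sample size is wrong or that the study is underpowered for its primary endpoint. The documents do not support that on this point: the calculation reproduces, and testing PASS first at the full 5% level preserves its power. Nor is there a type I error problem here, since a fixed sequence needs no adjustment of α.

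**What to change.** In Sample size and power considerations, replace the sentence that applies the calculation jointly to both objectives with two statements:

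1. 92% is the power of each test taken alone, and so the power for PASS as the first step of the hierarchy.
2. The power to claim both PASS and Quick-DASH MIC under that hierarchy is about 85–89% for correlations of 0 to 0.9 between the test statistics (84.6% at 0, 86.3% at 0.5, 88.3% at 0.8 and 89.3% at 0.9, for N = 992), taking 0.80 against 0.60 for both endpoints and ignoring weighting, missing data and crossover.

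If the sponsor has a basis for a particular correlation, it should be stated and the matching figure given. The cost is a sentence or two, made before data extraction. No patients, analyses or changes to N or to the testing order are needed; the only consequence is a less favourable stated power for the second objective.

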Adherence to the non-surgical intervention is assessed by the percentage of patients being referred for non-surgical treatment, and the actual number of patients with a minimum of 1 record, in the REDCap database, of receiving non-surgical intervention after the initial clinical examination: Adherence% = (Number of patients with a record of receiving non-surgical intervention/number of patients referred for non-surgical intervention) x 100. Treatment adherence will be presented with descriptive statistics (N, %) by randomisation group.

Patient's crossing over to receive surgery from the non-surgical intervention group within one year from allocation and patients from the surgical group without a record in the REDCap database of surgery performed will be considered a major protocol deviation. Furthermore, patients in both groups withdrawing from the trial between baseline and one year follow-up will be considered as a major protocol deviation. Minor deviations are not completing all follow-up measurement. The number (percentage) of patients with respectively major and minor protocol deviations will be summarised by treatment group. No formal statistical testing will be conducted.

Analysis populations

The primary analysis will be performed on the Intention-to-treat (ITT) population, including all eligible patients according to the treatment they were initially allocated (initial clinical decision at first medical examination) to receive. A sensitivity analysis will be considered based on the per-protocol population, if >5% of the total number of patients in one treatment group are major protocol violators. The per-protocol analysis set will include: 1) patients who in the surgical group were allocated (initial clinical decision at first medical examination) to receive surgery, and have a record of the surgery was performed in the REDCap database, including date and type of surgery performed, 2) patient who in the non-surgical group were allocated (initial clinical decision at first medical examination) to receive non-surgical treatment and a minimum of 1 record within 4 months, in the REDCap database, of receiving non-surgical intervention after the initial clinical examination as well as no record of surgery performed.

Trial population

Screening data

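### The SAP's major-deviation list omits a departure that its per-protocol set excludes: a non-surgical patient with no record of non-surgical treatment does not count toward the >5% trigger on that ground

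*SAP*

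**What the plan says.** The SAP section *Adherence and protocol deviations* names three major deviations:

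- In the non-surgical arm: "Patient's crossing over to receive surgery from the non-surgical intervention group within one year from allocation".
- In the surgical arm: "patients from the surgical group without a record in the REDCap database of surgery performed will be considered a major protocol deviation".
- In either arm: "patients in both groups withdrawing from the trial between baseline and one year follow-up will be considered as a major protocol deviation".

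The minor category has one entry: "Minor deviations are not completing all follow-up measurement". Both categories are to be tabulated by treatment group.

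The same section defines adherence in the non-surgical arm through "the actual number of patients with a minimum of 1 record, in the REDCap database, of receiving non-surgical intervention after the initial clinical examination", divided by the number referred for that care.

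*Analysis populations* makes the per-protocol analysis conditional: it applies "if >5% of the total number of patients in one treatment group are major protocol violators". To enter the per-protocol set, a non-surgical patient must have no surgery record and "a minimum of 1 record within 4 months, in the REDCap database, of receiving non-surgical intervention after the initial clinical examination". *Analysis methods* repeats the trigger and the set, but its version of the non-surgical criterion has no time window.

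**The concern.** A trigger for a per-protocol analysis should count the departures that the per-protocol set removes. Here it does so for the surgical arm, where a missing surgery record is both a major deviation and an exclusion. In the non-surgical arm, a missing treatment record is an exclusion but not a deviation of either kind.

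Two things are at stake. First, the per-protocol analysis is the only sensitivity analysis the SAP plans for the primary results, and *Additional analyses* says that nothing further is planned. Whether it runs depends on a count that leaves out one ground for exclusion in the arm expected to hold 930 of 992 patients (93.75%). Second, the deviation table by group would compare the arms on different definitions.

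**Working it through.** **Inputs.** *Sample size and power considerations* gives a total of 992 at 1:15, so 992/16 = 62 surgical and 930 non-surgical patients. The rates are 0.80 v 0.60 at two-sided 5%. The trigger is more than 5% in one group. The SAP gives no expected rate of untreated patients, crossover or withdrawal, so every such rate below is an assumption.

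**The plan's own figure.** The pooled proportion is (62 × 0.80 + 930 × 0.60)/992 = 0.6125. The standard error under the null is √[0.6125 × 0.3875 × (1/62 + 1/930)] = 0.0639. Under the alternative it is √[0.80 × 0.20/62 + 0.60 × 0.40/930] = 0.0533. Power is Φ[(0.20 − 1.96 × 0.0639)/0.0533] = 0.92, which matches the stated 92%. The arm sizes of 62 and 930 are therefore the plan's own.

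**Definitions side by side.**

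| Departure | Major deviation (counts toward trigger) | Outside the per-protocol set |
|---|---|---|
| Surgical, no surgery record | yes | yes |
| Non-surgical, surgery within one year | yes | yes |
| Non-surgical, no non-surgical record | **no** (nor minor) | **yes** |
| Withdrawal, either arm | yes | not stated |

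The third row is the point at issue. The fourth shows that list and set also differ in the other direction.

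**Trigger thresholds.** 0.05 × 62 = 3.1, so 4 surgical patients are needed. 0.05 × 930 = 46.5, so 47 non-surgical patients are needed.

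**What the omission does to the count.** Assume that 3% of non-surgical patients (0.03 × 930 ≈ 28) have a listed deviation and that a further 5% to 30% have no treatment record.

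- As written, the count is 28/930 = 3%, whatever the untreated share, and this arm does not fire.
- With the untreated counted, it is 930 × (0.03 + 0.05) ≈ 74 (8%) up to 930 × (0.03 + 0.30) ≈ 307 (33%), and it fires.

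**When this changes whether the analysis runs.** The omission matters for the trigger only if neither arm passes 5% on the listed deviations. With independent arms and one common rate p of listed deviations, the chance of that is P(X ≤ 3 | 62, p) × P(Y ≤ 46 | 930, p):

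| Assumed p | Surgical arm does not fire | Non-surgical arm does not fire | Neither fires |
|---|---|---|---|
| 4% | 0.764 | 0.936 | 72% |
| 5% | 0.624 | 0.509 | 32% |
| 6% | 0.485 | 0.097 | 4.7% |
| 7% | 0.361 | 0.006 | 0.2% |

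From about 6% upward the listed deviations almost always fire the trigger by themselves.

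**The case against.** The strongest reply is that little follows from the mismatch. The trigger fires if either arm passes 5%, and the listed deviations include a full year of withdrawals in both arms plus crossover. *Withdrawal/Follow-up* also classes loss to follow-up with consent withdrawal, so those patients may count too. A listed rate above 5% is quite possible, and the analysis then runs anyway. This stands, and it limits the consequence to the low-rate cases in the last table.

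A second reply is that untreated non-surgical patients are not hidden. Adherence is reported as N and % by group, and the *Recruitment* section has the flowchart show who received the allocated treatment. This also stands. The deviation table lacks one category, but the report as a whole discloses it.

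A third reply is that the non-surgical strategy is the decision not to operate, so a patient who takes up no care still complies with it. That is arguable in a pragmatic emulation, but the SAP's own adherence formula and per-protocol rule require a treatment record.

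Stronger readings are tempting but unsupported:

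- A reader might infer that untreated non-surgical patients can never count toward the trigger. They do count if they also withdraw or cross over within a year.
- A reader might infer from the 62% chance of 3 or fewer deviations among 62 surgical patients, at a true rate of 5%, that the surgical arm's trigger is broken by this asymmetry. That figure shows only how a cut-off behaves in a small arm when the true rate equals the cut-off. At a true rate of 10% the chance is 12%, and correcting the list does not alter the surgical count.
- A reader might infer that the primary result is at risk. It is not.

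**Conclusion.** The mismatch is real and can be read directly from the SAP. One treatment-based exclusion from the per-protocol set, no record of non-surgical intervention, is missing from the deviation list that drives the trigger and fills the deviation table. The unequal table definitions apply whatever the rates turn out to be.

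The effect on the trigger is conditional. It can change whether the per-protocol analysis runs only if listed deviations are about 5% or less in both arms, and only if enough non-surgical patients lack a record. The percentages assume 62 v 930 patients, independent arms and a common rate. The SAP supplies neither that rate nor the untreated share, so the size cannot be fixed more closely. The ITT population, the primary odds ratio and the gatekeeping order are untouched.

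**What to change.** First, reconcile the qualifying window for a non-surgical record. It is 4 months in *Analysis populations* and absent from both the adherence formula and *Analysis methods*. State one rule and use it in all places.

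Then add to the major deviations: *patients in the non-surgical group with no qualifying record of non-surgical intervention*. Every treatment-based per-protocol exclusion should then count toward the >5% trigger and appear in the deviation table for its arm. While editing, check the surgery criterion too: crossover is major only within one year, whereas the per-protocol rule requires no surgery record and sets no time limit.

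The cost is one added sentence and the alignment of the window. No new data are needed, because the adherence calculation already uses the same REDCap records. The SAP places data extraction after its own publication, so the change should be made before extraction. The downside is that the reported non-surgical deviation rate may rise and the sensitivity analysis may run more often.

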The total number of patients referred for examination due to suspicion of shoulder disorder, scheduled for an examination more than one week ahead and sent an electronic invitation, 2-4 days prior to their examination, in their personal electronic mailbox (E-boks) will be presented in the CONSORT flowchart (Figure 1) to describe the percentage of participation.

Eligibility

All patients, not in need of an interpreter at their medical examination, between 18 and 75 years, referred from private practice to the orthopaedic shoulder sector at Lillebaelt Hospital (Vejle) was invited.

Eligible patients: 1) diagnosed with shoulder disorder at initial medical examination; 2) had shoulder specific pathology on medical imagine; and 3) gave written consent to participate.

Patients were excluded if: 1) patients had significant cognitive impairment; 2) were unable to read and understand Danish; or 3) was diagnosed with diagnostic codes related to fracture of shoulder or upper arm; neurological conditions, disorders of the scapulae or frozen shoulder.

Recruitment

The CONSORT flowchart²⁵ will comprise number of patients invited, excluded (with reasons), eligible for inclusion in the trial, allocated (initial clinical decision at first medical examination), receiving their allocated treatment, withdrawals (with reasons), and lost to follow-up (with reasons), included in ITT analysis. The CONSORT flowchart is depicted in **Figure 1**.

Withdrawal/Follow-up

The level of consent withdrawal will be tabulated, classified as: 1) withdraw from follow-up but allow data collected to date to be used; 2) withdraw from follow-up and withdraw consent for data collected to date to be used; 3) lost to contact/follow-up. Timing of withdrawal will be presented with number and reasons in the CONSORT flowchart at the 3 months, 6 months and 1 year outcome assessment by treatment group.

Baseline patient characteristics

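### The >5% trigger for the per-protocol analysis does not count the same departures that define the per-protocol set, and the grade of a patient lost to follow-up is unclear

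*SAP*

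**What the plan says.** Under *Adherence and protocol deviations*, the SAP names three major deviations. Two concern treatment: crossing over to surgery from the non-surgical group within one year, and being in the surgical group without a record of surgery. The third concerns follow-up: "patients in both groups withdrawing from the trial between baseline and one year follow-up will be considered as a major protocol deviation". The next sentence reads "Minor deviations are not completing all follow-up measurement".

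Under *Withdrawal/Follow-up*, "The level of consent withdrawal will be tabulated, classified as" introduces three levels, of which the last is "3) lost to contact/follow-up". Under *Recruitment*, the flowchart instead shows "withdrawals (with reasons), and lost to follow-up (with reasons), included in ITT analysis", with withdrawals and losses as separate items.

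Under *Analysis populations*, and again under *Analysis methods*, the per-protocol sensitivity analysis depends on a threshold: "if >5% of the total number of patients in one treatment group are major protocol violators". The set itself is defined by treatment records. Surgical patients must "have a record of the surgery was performed in the REDCap database, including date and type of surgery performed". Non-surgical patients need at least one record "of receiving non-surgical intervention after the initial clinical examination as well as no record of surgery performed". Neither definition contains a follow-up criterion.

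*Missing data* handles missing one-year categorical outcomes by non-responder imputation. *Additional analyses* states that none are planned.

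**The concern.** There are two linked problems.

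First, consider a patient who stops answering without withdrawing consent. Under the withdrawal classification this is a withdrawal, and so a major deviation. Under the broad wording of the minor category it is incomplete follow-up, and so minor. The flowchart text leans towards the second reading. No rule says which grade prevails, so two analysts could produce different deviation tables from the same data.

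Second, the threshold is meant to detect enough departure from allocated treatment to make a per-protocol analysis worth running. Yet the events it counts are not the events that remove patients from the per-protocol set. The analysis can therefore be triggered when it has nothing to show, or be skipped when many patients would be excluded. It is the only sensitivity analysis in the plan.

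**Working it through.** **Step 1: trigger against set.** Each departure is checked against the list of major deviations and against the per-protocol definition.

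| Departure | Counts towards the >5% trigger | Removed from the per-protocol set |
|---|---|---|
| Surgical group, no record of surgery | yes | yes |
| Non-surgical group, surgery within one year | yes | yes |
| Non-surgical group, no record of non-surgical care | not listed | yes |
| Withdrawal before one year, treatment criteria met | yes | no |
| Lost to follow-up, treatment criteria met | unclear | no |

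The last three rows do not line up. A lost patient who meets the treatment criteria stays in the per-protocol set and is imputed as a non-responder for the categorical endpoints. Conversely, if 10% of the non-surgical group (93 of 930, an illustrative figure) had no record of non-surgical care and nothing else went wrong, the set would drop 93 patients while the trigger count stayed at 0.

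**Step 2: group sizes.** *Sample size and power considerations* gives 1:15 and N = 992, so 992/16 = 62 surgical and 930 non-surgical patients. To confirm this reading, the stated 92% power (0.80 v 0.60, two-sided 5%) is reproduced with the pooled-variance normal approximation:

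- Pooled proportion: (62×0.80 + 930×0.60)/992 = 0.6125
- Null SE: √[0.6125×0.3875×(1/62 + 1/930)] = 0.0639
- Alternative SE: √[0.16/62 + 0.24/930] = 0.0533
- Power: Φ[(0.20 − 1.96×0.0639)/0.0533] = Φ(1.40) = 0.92

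**Step 3: trigger counts.** The smallest count above 5% is floor(0.05n) + 1:

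- Surgical: floor(3.1) + 1 = 4, and 4/62 = 6.5%
- Non-surgical: floor(46.5) + 1 = 47, and 47/930 = 5.1%

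With N rounded up to 1000 (about 62 + 938), the counts are still 4 and 47.

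**Step 4: chance that loss alone trips the trigger.** The SAP gives no loss rate, so a range is shown. Assumptions: the same loss rate in both groups, independent patients, losses graded major, and no other major deviation. Let a = P(X ≥ 4) with X binomial (62, p), b = P(Y ≥ 47) with Y binomial (930, p), and either = 1 − (1 − a)(1 − b).

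| Assumed loss p | a (surgical) | b (non-surgical) | Either group |
|---|---|---|---|
| 1% | 0.004 | 0.000 | 0.004 |
| 2% | 0.036 | 0.000 | 0.036 |
| 3% | 0.116 | 0.000 | 0.116 |
| 5% | 0.376 | 0.491 | 0.682 |
| 10% | 0.879 | >0.999 | about 1 |

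For example, at 5% in the surgical group the probabilities of 0, 1, 2 and 3 losses are 0.042, 0.136, 0.218 and 0.229. They sum to 0.624, so a = 0.376. Then 1 − 0.624×0.509 = 0.682.

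If losses are graded minor, they contribute nothing and the chance is 0 throughout.

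**Step 5: how far the contrast depends on zero treatment departures.** The same tail applies to surgical patients without a surgery record. If that rate is 5%, the surgical group trips the trigger with probability 0.376 under either reading; at 10%, with probability 0.879. Once 4 surgical patients lack a record, or 47 non-surgical patients cross over, the grade given to losses no longer matters to the trigger.

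**The case against.** The two deviation grades stand in the same paragraph and can be read as a scale: leaving the trial is major, missing some measurements is minor. Everyone who withdraws also misses measurements, so overlap is natural and the higher grade would ordinarily prevail. The three-level list under *Withdrawal/Follow-up* is a tabulation rule that does not mention deviations. On this view the defect is one misplaced label. This stands in part: no sentence in the SAP calls a lost patient a minor deviation, and that status is only inferred from unrestricted wording. It does not settle whether loss counts as withdrawing, because the SAP's own two lists disagree.

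The consequence is also small. Membership of the per-protocol set does not depend on how losses are graded, so its estimate is the same under either reading. If every patient met the treatment criteria, the set would equal the ITT set and the extra run would merely repeat the primary result. That is harmless, although it would test nothing. This stands.

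Finally, part of the mismatch is independent of the ambiguity, since explicit withdrawal is major on any reading. That is correct, and it is why the fix should address the trigger and not only the label.

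A reader might go further and infer that loss will be the commonest departure, that deviation counts will differ several-fold between readings, or that the choice will be made once the data are seen. The SAP gives no loss or departure rates and puts data extraction after its own publication, so none of these is shown.

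**Conclusion.** The point holds as a minor one. The grade of a lost patient is unclear, and the >5% trigger is misaligned with the per-protocol set in both directions. It counts withdrawal (and possibly loss), which the set does not exclude, and it omits absent non-surgical care, which the set does exclude.

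What changes is whether the plan's only sensitivity analysis is run, and the content of the deviation table. It would be tempting to conclude that the trial's main finding is at risk. The documents do not support that: the primary ITT analysis and its non-responder imputation do not use these grades, and the per-protocol estimate does not move.

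The probabilities in the working rest on assumed loss rates, planned rather than actual group sizes, and no treatment departures. The contrast between readings shrinks as treatment departures approach 5% in either group. The misalignment itself rests on the text alone and needs none of these assumptions.

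**What to change.** 1. Let the >5% trigger count exactly the departures that define the per-protocol set: no record of surgery in the surgical group; surgery, or no qualifying record of non-surgical care, in the non-surgical group. Define a qualifying record once, because *Analysis populations* sets a four-month window that *Analysis methods* does not repeat.
2. Make major and minor deviations mutually exclusive, and state the grade of a patient lost to follow-up.
3. Take loss to follow-up out of the consent-withdrawal levels. Report consent withdrawal and loss to follow-up by group as separate missing-outcome categories, in line with the flowchart.
4. Reconcile the commitment: *Analysis populations* says the per-protocol analysis is to be considered when the threshold is passed, *Analysis methods* that it is to be performed.

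The cost is wording changes in *Adherence and protocol deviations*, *Analysis populations*, *Withdrawal/Follow-up* and *Analysis methods*, and an extra row in the deviation table. No new data are needed.
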